### **5.3 Recruitment**

The study is aimed to recruit a total of 25 male and female subjects having Type 2 Diabetes between ages 35 years or older. The recruitment will be performed through the Diabetes and Endocrinology Consultants of Pennsylvania, LLC (Decpa LLC) center. The clinic will identify patients that have done HbA1C test during the last 60 days and has HbA1C level as indicated in the inclusion criteria. These subjects will be approached by the clinic to participate in the study.

Each subject completes the study in 2 visits to the diabetes and endocrinology consultants center. The subject will receive a Diabetes health coaching which will include 2 monthly coaching sessions for a period of three months. The total study duration depends on the ability to enroll 25 subjects and is planned for three to four months.

## 6.0 Consent process

### 6.1 Screening Questionnaire

Potential candidate arriving at the study site will complete a screening questionnaire to verify his/her eligibility to be included in the study and to collect basic information including but not limited to: type of diabetes, age, gender, ethnicity, level of education, previous experience using smart mobile device, previous experience using BGMS, etc.

The screening questionnaire is provided in the CRF in **Appendix A**.

### 6.2 Informed Consent

Candidates found eligible for the study will receive an explanation by the investigator or delegate regarding the research nature of the study, the scope and aims of the study, the procedures to be followed and any discomfort that he/she may experience. The candidate will then be asked to read the informed consent form, ask any questions he/she may have and sign the form to indicate consent to participate in the study.

Written informed consent must be obtained from each study candidate. The form should be signed and dated by both the subject and the investigator or delegate. One copy of the signed consent will be given to the subject and the original will be retained by the site.

Subjects may withdraw their consent to participate in the study at any time without prejudice. The investigator may withdraw a subject if, in his clinical judgment, it is in the best interest of the subject or if the subject cannot comply with the protocol. Any withdrawal case should be fully documented in the CRF.

### 6.3 Medical Information

Demographic and medical information acquired verbally from the subject and through the screening questionnaire – including (but not limited to) age, gender, relevant medical information, concomitant medications, etc. – will be recorded in the CRF for all subjects participating in this study.

## 7.0 Study Conduct

### 7.1 Study Category

This clinical study is exempt from most provisions of the IDE regulation because it fits the category provided in 21 CFR 812.2(c)(3):

The Dario™ BGMS –

- *is properly labeled in accordance with 21 CFR 809.10(c);*
- *is noninvasive;*
- *does not require an invasive sampling procedure that presents significant risk;*
- *does not by design or intention introduce energy into a subject;*

and

- *is not used as a diagnostic procedure without confirmation of the diagnosis by another, medically established diagnostic product or procedure.*

## 7.2 Duration of Study

Each subject completes the study in 2 visits to the diabetes and endocrinology consultants center.

The total study duration depends on the ability to enroll up to 25 subjects and is planned for three to four months.

## 7.3 Device Accountability

Complete traceability records of all devices and accessories will be kept throughout the study.

Dario meter serial number and strip lot numbers, will be documented in subject's CRF. Additional material used during the study will also be recorded.

Subject will use their own smartphone. Only subjects with supported smartphones will participate in the study.

## 7.4 Protocol Deviation

Any deviation from the study protocol should be notified to the sponsor and fully documented on study deviation forms. Situations where the investigator anticipates, contemplates or makes a conscious decision to deviate from the protocol must be approved by the sponsor prior to deviation. Situations where unforeseen circumstances are beyond the control of the investigator's control (product failure, patient illness, etc.) and/or where the investigator needs to protect the subject's life or physical well-being in an emergency do not require prior sponsor approval.

## 7.5 Protocol Modification

An amendment to the protocol may be proposed to the sponsor by the clinical site staff. The amendment will be prepared and approved by the sponsor. The amendment must be

---

 According to 21 CFR 812.3(k), blood sampling that involves simple venipuncture is considered noninvasive.

submitted to the IRB. When applicable, the amendment's implementation will take place only once approved by the IRB.

## **7.6 Confidentiality**

Each subject will be identified by his/ her initials and a unique subject identification number. Source data will be stored with source documents. The Study Site File (SSF) will be held in a secure area. The subject's name and personal data will remain confidential and will not be published in any way. However, the sponsor's representative and regulatory representatives, auditors and inspectors may have access to medical files in order to verify authenticity of the collected data.

## **7.7 Record Retention**

It is the investigator's responsibility to retain study essential documents for at least 5 (five) years after the clinical study.

## **7.8 Case Report Forms**

The study case report form (CRF) is the primary data collection instrument for the study. All data requested on the CRF must be recorded. All entries in the CRF should be printed legibly using ballpoint pen (no pencil). If any entry error has been made, such an error should be corrected by drawing a single straight line through the incorrect entry and entering the correct data above it. All such changes must be initialed and dated by the person making the change. Erasing or whiting-out errors is prohibited.

The following abbreviations should be used:

- If the answer to a question is unknown, write 'UNK' (Unknown)
- If a question is not applicable, write 'N/A' (Not Applicable)
- If a requested task has not been done, write 'ND' (Not Done)

Completed CRF must be signed and dated by Investigator confirming the accuracy and completeness of data entries.

## **7.9 Study Funding**

The study is funded by LabStyle Innovation Ltd.

# **8.0 Adverse Events**

All adverse events (AE) occurring during the study will be recorded on the appropriate case report form page by the nurse/technician. The nature, severity and relation of the

adverse event to the study device will be documented. The PI will sign the adverse event form.

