## Protocol Synopsis

Protocol Title:	Digital Self-Management and Health Coaching for Type 2 Diabetes - Impact on Diabetes clinical and wellbeing indicators
Protocol ID:	CP-0010
Principal Investigator:	[name] [name] [contact] Email: [name] <[contact]>
Sponsor:	LabStyle Innovation (LSI) [name]
Sponsor Representative:	[name] [contact] E-mail: [contact]
Product to be Evaluated:	Dario Blood Glucose Monitoring System (BGMS) and connected cloud platform
Research Center:	Diabetes and Endocrinology Consultants of Pennsylvania, LLC (Decpa LLC) [name]
Research Center Representative:	[name]
Data Management & Statistics:	LabStyle Innovation (LSI)
Study Objectives:	To evaluate the impact of the Dario digital self-monitoring platform provided with diabetes management coaching on: 1. Individual's Quality of Life for 2. Clinical parameters (HbA1C, weight, lipids profile, etc.) For people with Type 2 Diabetes at end of study vs. baseline.
Study Design:	single-arm
Study Type	Interventional, Behavioral

Study Specimen:	Lab test Venous blood - Blood glucose level and HbA1C Self-test Capillary whole blood - Blood glucose level
Study Procedures:	Each subject enrolled in the study will be requested to complete an intake questionnaire including diabetes quality of life questions. The subject will use Dario Blood glucose monitoring system and will be contacted by a Certified Diabetes Educator (CDE) two to three times a month as well as have a direct communication using other communication channels such as mail, chat and text messaging (SMS) for lifestyle and diabetes management coaching for a total duration of three months. In the end of study, the subject will complete a diabetes quality of life questionnaire and have a blood test to evaluate its clinical parameters.
Study Population:	Males and females with type 2 Diabetes, ages above 35 recruited through clinic, physician offices, and similar sources having HbA1c level of 8.5% or more, verified by last lab test performed during the last 60 days
Number of Visits	2 visits only
Sample Size:	25 subjects

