## 2.0 Device Information

### 2.1 Device Name

Dario Blood Glucose Monitoring System (BGMS) with Dario digital platform providing access to patient's clinical information and logged behavior captured in the BGMS Application (app).

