# 3.0 Study Objectives

To evaluate the impact of the digital self-monitoring platform provided with diabetes management coaching on:

1. Individual's Quality of life
2. Clinical parameters (HbA1C, weight, lipids profile, etc.)

For adults with Type 2 Diabetes at end of study vs. baseline

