## **4.0 Study Design and Procedure**

### **4.1 Study Description**

This study is designed to assess the effect of digital self-monitoring platform used with the remote support of a Health coach on clinical outcomes and Diabetes quality of life. Study design will be an open-label randomized trial of adults with Type 2. Patients are recruited through the Diabetes and Endocrinology Consultants center setting. Upon randomization to the intervention group, study participants will receive three months diabetes health coaching comprising of:

1. Two scheduled phone sessions with a Diabetes health coach a month;
2. Ongoing dual communication with the coach using digital communication channels such as chat, SMS and emails
3. Diabetes education, behavior modification, goal setting and reinforcement.

The Dario App will record participant's glucose measurements and additional information captured by the patient such as medication intake, food and physical activity results. The coach will get access to the patients' App captured information and will intervene ad necessary in the context of the clinical information.

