### **8.1 Definitions**

*Adverse Event (AE)* means any undesirable experiences (sign, symptom, illness, or other medical event) occurring to a subject, whether or not associated with the investigational product or related procedures.

*Serious Adverse Event (SAE)* means any adverse event experience that results in any of the following outcomes: death, a life-threatening adverse experience, inpatient hospitalization or prolongation of an existing hospitalization, a persistent or significant disability/incapacity, permanent impairment of a body function or permanent damage to a body structure, or necessitated medical or surgical intervention to preclude permanent impairment of a body function or permanent damage to a body structure.

*Unanticipated Adverse Device Effect (UADE)* means any serious adverse effect on health or safety or any life-threatening problem or death caused by, or associated with, a device, if that effect, problem, or death was not previously identified in nature, severity, or degree of incidence in the investigational plan or application (including a supplementary plan or application), or any other unanticipated serious problem associated with a device that relates to the rights, safety, or welfare of subjects.

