### **8.5 Expedited Reporting of SAE**

In the unlikely occurrence of a serious adverse event, such event must be reported to the sponsor within 24 hours of investigator's/delegate's knowledge of the event by calling or emailing the information to:

[name]  
[contact]  
E-mail: [contact]

If applicable, the investigator should also inform the representative of the IRB within 24 hours of becoming aware of the event. A copy of the report cover letter should be filed in the SSF.

The sponsor is responsible for the ongoing safety evaluation of the device and, if applicable, communicating the information with the FDA.

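### Relatedness of adverse events is to be judged against the device only, although the intervention under test is the platform plus coaching

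*Combined protocol and SAP*

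**What the plan says.** The causality instruction is one sentence in section 8.0. It begins "The nature, severity and relation of the" and ends "adverse event to the study device will be documented". Section 8.5 adds: "The sponsor is responsible for the ongoing safety evaluation of the device".

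Section 2.1 names the device as "Dario Blood Glucose Monitoring System (BGMS) with Dario digital platform providing access to patient's clinical information" and the behaviour logged in the app. The coach's advice is not listed as part of it.

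The object of the study is wider. The synopsis states it as "To evaluate the impact of the Dario digital self-monitoring platform provided with diabetes management coaching on" quality of life and clinical parameters, and section 3.0 repeats this. Section 4.1 lists among the coaching components "Diabetes education, behavior modification, goal setting and reinforcement". Section 4.3 says that the coaching will be based on what the app records, including glucose readings, activity and carbohydrates.

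The definition of an adverse event in section 8.1 is broad: it covers events "whether or not associated with the investigational product or related procedures". Section 8.5 requires serious adverse events to reach the sponsor within 24 hours and sets no condition on relatedness.

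**The concern.** The study will credit any benefit to the platform and the coaching together, but its safety text asks about harm from only one of the two. The coaching aims to change what people with poorly controlled diabetes eat and do, so it is a plausible cause of harm in its own right.

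Suppose an insulin user has a low-glucose episode after acting on a coached food or activity goal, and the meter read correctly throughout. (The synopsis lists insulin treatment among the data to be collected, so such subjects are expected.) Asked only whether the event was related to the device, a careful investigator could answer no. Nothing in section 8 then links the event to the coaching or calls for the coaching to be looked at. A later statement that few or no events were related would be silent on the coaching.

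**Working it through.** No figure in the plan bears on this point and there is nothing to recompute. The check sets what is tested against what each safety provision covers.

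| Provision | Where | Device or platform | Coaching |
|---|---|---|---|
| Intervention evaluated | Synopsis, 3.0, 4.1 | Yes | Yes |
| Before-after comparison | 9.2 | Yes | Yes |
| Capture of adverse events | 8.0, 8.1 | Yes | Yes, any event |
| Relation to be documented | 8.0 | Yes | Not named |
| Unanticipated adverse device effects | 8.1, 8.2 | Yes | Not named |
| Malfunction reports | 8.2 | Yes | Does not apply |
| Anticipated events | 8.3 | Finger prick and blood sampling | None listed |
| Serious events to the sponsor in 24 hours | 8.5 | Yes | Yes, regardless of relation |
| Ongoing safety evaluation | 8.5 | Yes | Not named |

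1. **Capture is adequate.** Sections 8.0 and 8.1 bring in every event, and 8.5 sends every serious one to the sponsor. An event caused by coaching would be on file.
2. **Attribution is not.** The device is the only stated object of the causality judgement. No passage asks for relation to the coaching, to the combined programme or to study procedures.
3. **Review follows the same line.** The ongoing evaluation in 8.5 is of the device. Nothing in section 8 directs anyone to consider whether the coaching is causing harm.
4. **The design offers no substitute.** The synopsis describes a single-arm study. Section 4.1 speaks of randomization, but the only analysis in 9.2 is a paired comparison with baseline. With no planned comparator to show an excess of events, case-by-case judgement is the main route to attributing harm.
5. **Section 8.3 suggests that the safety text was not fitted to this intervention.** It limits the anticipated events on the premise that the device is confined to the clinic and that its readings do not inform treatment. The synopsis and sections 4.1 and 4.3 describe three months of self-monitoring with coaching driven by the recorded data. These passages contradict each other and must be reconciled.

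**The case against.** The case on the other side has several parts.

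- **The form is not visible.** The adverse event form belongs to the case report form in Appendix A, of which only the heading can be read. Section 8.0 sets what must be documented and does not say that the form has no other field. This stands: the point rests on the protocol text alone.
- **A coaching event might be rated device-related.** Section 2.6, within the device chapter, presents the platform as the means by which the coach intervenes, and the definition of an unanticipated device effect in 8.1 covers association as well as cause. This also stands. A reader might infer that events from coaching will necessarily be recorded as unrelated, but the text is ambiguous and does not force that. The ambiguity is itself a reason for a separate category, since a device-related rating could blame a meter that worked correctly.
- **The sponsor still sees the events.** Besides the 24-hour rule, the sponsor monitors at three points with access to all study documents (10.1) and is entitled to all data (12.0). A reader might infer that such events escape the sponsor altogether; the documents do not support this. Access to a record is nevertheless not an instruction to judge whether coaching caused the event.
- **No planned table is affected.** Sections 4.2 and 9.2 contain no safety outcome and no count of related events, so it cannot be said that events drop out of one. This stands. The risk lies in what may later be said about relatedness and in the absence of a trigger for review.

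**Conclusion.** The point holds as a gap in attribution and review. Under the protocol text, relation is documented to the device only and the sponsor's continuing evaluation is of the device only, while the tested intervention includes coaching. An event caused by acting on coaching could be rated not related, with no other attribution provided.

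The size cannot be stated in numbers. The gap applies to any adverse event in up to 25 subjects in which coaching played a part, but the documents give no event rate and no basis for estimating how many there would be. A reader might take the number of coaching sessions as a measure; that is exposure, and it says nothing about how many events would be misattributed.

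The conclusion assumes that section 8.0 governs the form. If the form already asks about coaching, the remaining defect is that sections 8.0 and 8.5 do not match it. No planned efficacy analysis changes. This is a low-cost safety improvement that should be made.

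**What to change.** - In 8.0, have the investigator record relation separately to (a) the device or platform, (b) the coaching and (c) study procedures, and make the Appendix A form match.
- In 8.5, extend the sponsor's ongoing safety evaluation to the device and the coaching programme.
- Add to section 9.2 that adverse events will be reported by these three categories.
- Reconcile the premise of 8.3 on where the device is used and what its readings inform with the synopsis and sections 4.1 and 4.3, then review the list of anticipated events in that light.

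The cost is a slightly longer form and a few sentences of text. Visits, sample size and the efficacy analysis are untouched. The count of events judged related to some part of the programme may look less favourable.

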### **8.1 Definitions**

*Adverse Event (AE)* means any undesirable experiences (sign, symptom, illness, or other medical event) occurring to a subject, whether or not associated with the investigational product or related procedures.

*Serious Adverse Event (SAE)* means any adverse event experience that results in any of the following outcomes: death, a life-threatening adverse experience, inpatient hospitalization or prolongation of an existing hospitalization, a persistent or significant disability/incapacity, permanent impairment of a body function or permanent damage to a body structure, or necessitated medical or surgical intervention to preclude permanent impairment of a body function or permanent damage to a body structure.

*Unanticipated Adverse Device Effect (UADE)* means any serious adverse effect on health or safety or any life-threatening problem or death caused by, or associated with, a device, if that effect, problem, or death was not previously identified in nature, severity, or degree of incidence in the investigational plan or application (including a supplementary plan or application), or any other unanticipated serious problem associated with a device that relates to the rights, safety, or welfare of subjects.

### **8.2 Reporting Requirements**

According to the study category (see **Error! Reference source not found.**), the reporting requirements appropriate for this study are provided in 21 CFR 812.150(b) (1):

*“Unanticipated adverse device effects. A sponsor who conducts an evaluation of an unanticipated adverse device effect under § 812.46(b) shall report the results of such evaluation to FDA and to all reviewing IRB’s and participating investigators within 10 working days after the sponsor first receives notice of the effect. Thereafter the sponsor shall submit such additional reports concerning the effect as FDA requests.”*

Additionally, the clinical site staff is required to report all possible device malfunctions or failures observed during the study. These incidents will be documented in the relevant page of the CRF.

---

 21 CFR § 812.3(s)

### **8.3 Anticipated Adverse Events**

Anticipated adverse events for the Dario™ BGMS include those that are reasonably expected to occur in association with any other type of commercially available BGMS intended for home use, which includes local pain at the finger prick site. Due to the fact that the device will be used only at the site and its results will not serve for treatment decisions, there are no other anticipated adverse events.

Additional anticipated adverse events that may occur in the study are these associated with obtaining capillary blood sample e.g., local pain at needle insertion site, small hematoma, etc.

### **8.4 Adverse Event Recording**

All adverse events occurring during the study must be recorded by the investigator or delegate on the appropriate AE form in the subject's CRF within a reasonable time (up to 5 calendar days from being aware of the event).

### **8.5 Expedited Reporting of SAE**

In the unlikely occurrence of a serious adverse event, such event must be reported to the sponsor within 24 hours of investigator's/delegate's knowledge of the event by calling or emailing the information to:

[name]  
[contact]  
E-mail: [contact]

If applicable, the investigator should also inform the representative of the IRB within 24 hours of becoming aware of the event. A copy of the report cover letter should be filed in the SSF.

The sponsor is responsible for the ongoing safety evaluation of the device and, if applicable, communicating the information with the FDA.

